**Table 2. Power for Contrasts of Interest** 

Specific Aim	Contrast	Contrast (Table cell)	Stipulated Effect size(sd)			Estimated Power
			Р	S	P,S	
1a	S+ v S-	a,b vs c,d	0.5	0.5	0.1	0.90
1a	P+ v P-	a,c vs b,d	0.25	0.25	0.1	0.95
1b	S+P+ v S-P+	a vs c	0.5	0.5	0.1	0.95
1b	S+P+ v S+P-	a vs b	0.35	0.5	0.0	0.88
1b	S- P+ v S+P-	b vs c	0.75	0.25	0.0	0.92
1c	S+P+ v S-P-	a vs d	0.25	0.25	0.1	0.96
1c	S- P+ v S-P-	c vs d	0.35	0.5	0.0	0.90
1c	S+P- v S-P-	b vs d	0.5	0.5	0.1	0.90
20%	Subgroup					
2a	S+ v S-	a,b, vs c,d	0.5	0.6	0.1	0.83
2a	P+ v P-	a,c vs b,d	0.5	0.6	0.1	0.88

P=Primary care effect; S=School Effect; PS= interaction; "+" = , "-" = control

Cells e, f are not included in this table for simplicity and to be conservative.

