5.5 Original power estimates for planning purposes

Power calculations are for planning purposes only. The following paragraph is historical information only.

The following description and table report power calculations as originally planned for the study design. Alternative power calculations for fewer patients appear later.

All power estimates are based on custom programmed simulations. All power estimates represent changes over time in the primary outcomes (asthma control) in units of standard deviation of change. For translation into clinical terms, the minimally important difference (MID) for children on the Juniper's Asthma Control Questionnaire is 0.5 standard deviation units, which equates to 0.4 units on the questionnaire scale (for children ages 6 to 17 years). (Nguyen 2014). The power simulations assumed a modest degree of variation in outcomes across schools, which equates to clustering of children within schools. For an overall effect size of 0.5 standard deviation units, we assumed that individual schools would vary from no effect (0.0) to a large effect (1.0sd units). This degree of variation coefficient (ICC) of 0.06. With an average of 28 children per school, this variability equates to a design effect (variance inflation factor) of about 2.5. As the table shows, the contrasts for the navigator intervention are powerful to show even small effects, because they are within-cluster comparisons and therefore are influenced if at all only slightly by clustering of children within schools. Across school contrasts, of the effects of the school intervention, remain powerful for MID changes.

Specific	Contrast	Contrast	Stipula	ted		Estimated
Aim		(Table cell)	Effect size(sd)		Power	
			А	S	A,S	
1a	S+ v S-	a,b vs c,d	0.5	0.5	0.1	0.90
1a	A+ v A-	a,c vs b,d	0.25	0.25	0.1	0.95
1b	S+A+ v S-A+	a vs c	0.5	0.5	0.1	0.95
1c	S- A+ v S+A-	b vs c	0.75	0.25	0.0	0.92
1d	S+A+ v S-A-	a vs d	0.25	0.25	0.1	0.96
	S- A+ v S-A-	c vs d	0.35	0.5	0.0	0.90
	S+A- v S-A-	b vs d	0.5	0.5	0.1	0.90
20%	Subgroup					
2a	S+ v S-	a,b, vs c,d	0.5	0.6	0.1	0.83
2a	A+ v A-	a,c vs b,d	0.5	0.6	0.1	0.88

Table Y. Power for contrasts of interest.

A=Navigator effect; S=School Effect; AS= interaction; "+" = , "-" = control Cells e, f are not included in this table for simplicity and to be conservative.

6 Analysis of subgroups

Specific Aim 2: Explore moderators and mechanisms of effectiveness of the asthma navigator and school-based asthma therapy interventions.

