6.1 *Heterogeneity of treatment effect -- Effect modification (moderators)*

Effect modifiers are factors that reflect differences in the effect of the intervention across subgroups of children and/or schools. When taken together these child or school level factors can describe those children or schools that are predicted to do better or worse than the reference group of schools or children. "For a clinical trial that establishes treatment efficacy in its overall population, investigating consistency of treatment effects across subgroups is important for interpreting the efficacy findings and consequently for determining the appropriate population for treatment use." (Alosh 2017) Effect modification is to be distinguished from program interaction, which in this factorial-design trial will estimate the degree to which the combination of child and school level interventions achieves synergy (or antagonism).

As subgroup analysis is fraught with problems of multiple comparisons, we shall adhere to the following principles for analysis and reporting: pre-specification of subgroups of interest, focus on subgroups that are clinically important as suggested by prior research, and attention to considerations of statistical power for identifying subgroups.

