6.1.5 Statistical software considerations

Methods for longitudinal analysis apply equally well to comparison of subgroups and to assess heterogeneity of treatment effects. Latent class analysis is available in SAS and more recently in Stata v15 et seq in "gsem", a program that will allow for different types of variables using to create latent classes. Python may also be used in sensitivity or primary analyses (Couronne, Vidailhet, Corvol et al. 2019).

6.1.6 Statistical Power for effect modification:

Owing to the absence of software for testing interaction effects, these estimates are based on our simulations conducted during the study design phase using Stata v 14.1. For a subgroup as small as 20% of the expected students (n=600) or 120 children, our design has 88% power to detect the effect of the navigator and 83% power to detect the effect of school for effect sizes of 0.5 for navigator, 0.6 for school, and a small interaction of 0.1.

This preliminary estimate does not anticipate issue of multiple comparisons. To the extent that the study reports differences in outcomes by baseline groups, simple Bonferroni corrections will apply.

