6.3 Statistical power for mediation analysis

The original study design included the following power calculations:

For this Aim, we rely on two programs contributed to the R statistical package. We again assumed 600 evaluable patients across 23 schools, and a design effect of about 2.5. In brief, David Kenny's program "PowMedR" (Kenny 2014) suggests that power is adequate to detect an effect size (in terms of standard deviations) of 0.25 sd for both the effect of the navigator intervention (A) on the mediator (M) and the effect of M given A on Y (conditional effect of M on outcome). Likewise, for the effects of school (S), with a design effect (variance inflation) of 2.5 (see estimate above based on ICC), power remains adequate for detecting an effect size of 0.5, which is the minimal important difference for asthma control For confirmation, the R package "medssp" (VIttinghoff 2015) suggests adequate power (greater than 0.8) to detect effect sizes of 0.25 jointly and separately for both the association of A (navigator) and M (effect of intervention M) and the effect of M on Y, and to detect effect sizes of 0.6 for the association of S (school based intervention) and M, the difference owing to the large design effect (variance inflation) arising from the clustered randomization of schools.

These calculations do not consider the impact of multiple comparisons and the change in the critical alpha level for these estimates. Power will quickly degrade with more than a few candidate mediators (updated 07/16/2019)

7. Analysis for implementation

See Penn IRB. (IRP PROTOCOL#: 830021. Adoption and Implementation of West Philadelphia Asthma Care Implementation Plan)

8. Power Calculations - revised 04/2019

Primary outcomes

Initial designs included formal statistical power calculations. Based on initial recruitment rates, the initial power calculation (for design and planning purposes) has been replaced by the following update (dtd 04/14/2019). Power calculations were done for planning purposes only, and they are here for historical record keeping purposes only. They are not appropriate once the study has been done. What happens if the number of children to be recruited falls below originally planned?

Factorial design		Child-level Intervention	
		A+	A-
School	S+	a	b
Level	S-	c	d
	none	e	f

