The proposed design results in 6 groups of children. The cells a,b,c,d will permit comparison of any of the 3 combinations of school (S+) and child (A+) interventions (a,b,c) against the group that has neither(d). At the same time, it will permit marginal analysis of the effect of the school intervention (a+b vs c+d), and the marginal effect of the navigator intervention (a+c+e vs b+d+f).

For each of the cells of interest, we collect baseline data on children and then follow schools and children over time. This design avoids contamination and interference through cluster randomization, but benefits from added power of a longitudinal analysis. The factorial layout permits estimation (and testing) of interaction between the school and individual interventions. It also allows for use of data from children who are from nonparticipating schools.

This report focuses on the project power of a somewhat lower number of recruits in the 4 cells: a,b,c, and d, with a current projection of about 100 per cell (children) as contrasted with the prior expectations of 150 per cell. The design has also changed in that we now have more sites (expected 36 sites, with 18 in S+ and 18 in S-, the school-level intervention and controls.

As before, we could not rely on commercial power programs because of the complexity of the design – a convention randomization scheme crossed with a cluster randomized trial (school intervention). For that reason, we again report the results of simulation of the expected power given a stipulated "effect size" for the treatments (A+ and S+) at the child and school levels.

Another reason for the simulations is that we are interested in particular contrasts of interest in the effects of S+ and A+

Reviewing the prior assumptions from 2016 design.

Earlier power calcs were done by [name] by simulation, which posed a 2 by 2 factorial design with A=patient level and S=school level intervention. Estimates assumed a continuous outcome (such as asthma control) and improvement over time (to simplify the longitudinal data design).

We assumed factorial terms of A and S main effects and A*S interaction.

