The main effects of A and S take into account that any interaction will affect the main effects. If the interaction is synergistic, then the "main effects" will be larger than just the A term or the S term alone. Main effects in this context are the marginal effects (of A and S), and these marginal effects are larger if there is a synergistic interaction (if the interaction is negative, then of course, the marginal effects are smaller).

We assume a design effect for the S+ S- effect (cluster randomized, and now 36 clusters (18+ 18)). If we assume effect size variation across sites (schools) of 0.0 to 0.5, then sd of random intercept is about 0.125. That would mean that if sigmasq= 1.0, then sigmasq(b) = 0.125*0.125. =0.016. If we assume that the variation in effect size is broader (0 to 1.0), then sd= 0.25 and sigmasq(b) = 0.25*0.25 = 0.0625. We used this broader assumption. Then ICC = 0.0625/(1.0625) = 0.06 and DEFF= 1+0.06*11 (assuming cluster size = 12) = 1+0.66= 1.66.

Plan is as follows.

Using program from Oct 2016, recreate power with 36 sites and 12 patients per site (n=432 overall). Results appear in the Table below.

Contrast	Contrast	Stipulated			Power	Power
	(Table cell)	Effect size(sd)			(n=600)	(n=432)
		А	S	A,S		
S+ v S-	a,b vs c,d	0.35	0.5	0.0	0.96	0.97
A+ v A-	a,c vs b,d	0.35	0.5	0.0	0.99	0.95
S+A+ v S-A+	a vs c	0.35	0.5	0.0	0.89	0.88
S+A+ v S+A-	a vs b	0.35	0.5	0.0	0.87	0.75
S- A+ v S-A-	c vs d	0.35	0.5	0.0	0.85	0.71
S+,A- v S-A-	b vs d	0.35	0.5	0.0	0.89	0.83
		А	S	A,S		
S+ v S-	a,b vs c,d	0.35	0.5	0.25	0.99	0.99
A+ v A-	a,c vs b,d	0.35	0.5	0.25	0.99	0.99
S+A+ v S-A+	a vs c	0.35	0.5	0.25	0.99	0.99
S+A+ v S+A-	a vs b	0.35	0.5	0.25	0.99	0.99
S- A+ v S-A-	c vs d	0.35	0.5	0.25	0.85	0.71
S+,A- v S-A-	b vs d	0.35	0.5	0.25	0.89	0.83

Power for contrasts of interest. Effect sizes are in terms of Cohen's d nomenclature and represents the fraction of standard deviations of change over time.

A=Navigator effect; S=School Effect; AS= interaction; "+" = , "-" = control

Cells e, f are not included in this table for simplicity and to be conservative.

Power to detect main effects

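### SAP 6.1.6 presents within-subgroup treatment power at the design-phase n=600 (88% and 83%) as power for effect modification, and 6.1.2.1 contradicts 9.2 on the same subject

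*SAP*

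**What the plan says.** SAP 6.1 sets the definition: "Effect modifiers are factors that reflect differences in the effect of the intervention across subgroups of children and/or schools". It separates this from the navigator-by-school interaction, which it calls program interaction.

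SAP 6.1.6 is headed as power for effect modification and opens: "Owing to the absence of software for testing interaction effects, these estimates are based on our simulations conducted during the study design phase". It then takes 20% of 600 children, i.e. 120, and says that "our design has 88% power to detect the effect of the navigator and 83% power to detect the effect of school", for effects of 0.5 (navigator), 0.6 (school) and 0.1 (interaction). It calls the estimate preliminary and says that multiple comparisons are not allowed for.

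The same 0.88 and 0.83 stand in SAP 5.5, Table Y, which is introduced with "The following description and table report power calculations as originally planned for the study design", and in Protocol 6.4, Table 2. In both tables they appear under a 20% subgroup label, as A+ v A- (P+ v P- in the Protocol) and S+ v S-.

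SAP section 8 says that "the initial power calculation (for design and planning purposes) has been replaced by the following update". The update is to "recreate power with 36 sites and 12 patients per site (n=432 overall". It has no subgroup rows.

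On adequacy the SAP says two things. Section 6.1.2.1 treats effect-modifier contrasts as within-school comparisons, credits them with good power and points forward in the text. Section 9.2 says that attempts to show heterogeneity or mediation will very likely all fail because there are too few patients.

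SAP 6.1.3, on bootstrap intervals for subgroups, equates the 399th and 999th order statistics with the 2.5th and 97.5th percentile bounds.

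**The concern.** A reader who goes to 6.1.6 for the power of the Aim 2a moderator analyses finds 88% and 83%. Under that heading, a moderator analysis that shows no difference looks like reasonable evidence that the effect is consistent across children. Read against 9.2, the same result says very little. Both statements stand in a SAP finalised in September 2022, and the forward reference in 6.1.2.1 leads to 6.1.6, so the mislabelled figure props up the more optimistic of the two.

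The order-statistic sentence in 6.1.3 is a separate slip with no bearing on power. Anyone who coded the interval from it literally would get the wrong bounds.

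**Working it through.** **Inputs.** Subgroup 20%; 600 children (SAP 6.1.6) or 432 in 36 schools (SAP 8). Effects 0.5, 0.6 and interaction 0.1 (6.1.6). SAP 8 treats main effects as marginal, so navigator = 0.5 + 0.1/2 = 0.55 and school = 0.6 + 0.1/2 = 0.65. ICC 0.06 and between-school variance 0.0625 (SAP 5.5 and 8). Schools at n=600: 600/28, about 21 (SAP 5.5), or 23 (SAP 6.3). Assumed: two-sided 0.05, SD 1, 1:1 allocation, power = Φ(d/SE − 1.96).

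**1. The plan's own figures, read as contrasts inside 120 children.**
- Navigator: SE = √(4/120) = 0.1826; 0.55/0.1826 gives power 0.854. With residual variance 0.94 (1 − ICC) it is 0.874. Stated: 0.88.
- School, 21 schools, m = 120/21 = 5.71 children each. Form A: SE = √(4/21 × (0.0625 + 1/5.71)) = 0.2127. Form B: SE = √(4/120 × (1 + 4.71 × 0.06)) = 0.2068. Power is 0.805 to 0.882 by z for effects of 0.60 and 0.65, and 0.763 to 0.846 by t on 19 df. Stated: 0.83.

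Both figures are reproduced closely as within-subgroup contrasts.

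**2. The rival reading, a treatment-by-subgroup test (120 v 480).** With no school-by-subgroup variation, SE = √(4/120 + 4/480) = 0.2041 for either factor. The larger school effect would then have the higher power: 0.84 for 0.6 against 0.69 for 0.5, or 0.89 for 0.65 against 0.77 for 0.55. The plan's order is the reverse (navigator 0.88, school 0.83). The figures are therefore not between-subgroup power, which is also what the table rows say.

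**3. The same within-subgroup contrasts at n=432 (86.4 children, 2.4 per school).**
- Navigator, cells a to d: SE = √(4/86.4) = 0.2152, power 0.724, down from 0.854.
- School: form A SE = √(4/36 × (0.0625 + 1/2.4)) = 0.2307; form B SE = √(4/86.4 × (1 + 1.4 × 0.06)) = 0.2240.

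| School, form and effect | n=600, 21 schools: z (t) | n=432, 36 schools: z (t) |
|---|---|---|
| A, 0.60 | 0.805 (0.763) | 0.739 (0.714) |
| A, 0.65 | 0.863 (0.826) | 0.804 (0.781) |
| B, 0.60 | 0.827 (0.786) | 0.764 (0.740) |
| B, 0.65 | 0.882 (0.846) | 0.827 (0.805) |

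Every variant falls, by about 4 to 7 points. Starting from 23 schools the fall is about 5 to 8 points.

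**4. Illustration of a between-subgroup difference.** The SAP specifies neither a split nor a difference, so both are assumed: 20/80, and a navigator effect of 0.55 confined to the smaller group. At n=600, 0.55/0.2041 gives 0.77. At n=432, SE = √(4/86.4 + 4/345.6) = 0.2406 and power is 0.63. Both are before Bonferroni.

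**5. Order statistics.** The 399th of 399 and the 999th of 999 are the maxima. The percentile bounds are 0.025 × 400 = 10 and 0.975 × 400 = 390, or 0.025 × 1000 = 25 and 0.975 × 1000 = 975.

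**The case against.** The body of 6.1.6 describes its quantity fairly: a subgroup of 120, and power for the effect of each intervention. It discloses n=600, the design phase and the lack of a multiplicity allowance. Effects within subgroups are themselves planned (SAP 6.1.2 and 6.1.2.2), so the figures are relevant to Aim 2a. The interaction in its opening sentence may mean navigator by school, since the 0.1 that follows is that term. All this stands, and it narrows the fault to the heading and lead-in. It does not make the figures power for what 6.1 defines.

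Sections 5.5 and 8 call power figures planning or historical material, the section 8 update is labelled for primary outcomes, and Protocol 3.3.2 still expects at least 600 evaluable children. These are good reasons not to demand a new power calculation, and Bonferroni explains part of the distance from 9.2. They do not reconcile 6.1.2.1 with 9.2.

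Three further readings are tempting, and the documents do not support them.
- That 88% and 83% are miscalculated. They are close to what the stated inputs give for their own contrasts.
- That school power inside the subgroup is unaffected by the smaller size. Section 8 does report school power as unchanged, but for full-sample contrasts. Setting an approximation at n=432 beside the plan's simulated 0.83 does not compare like with like; the same formula at both sizes shows a fall.
- That a definite power for moderation can be quoted. The SAP plans latent classes and fixes neither their number nor a difference.

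**Conclusion.** The point holds as one of labelling and consistency. The 6.1.6 figures are design-phase power for treatment contrasts inside a 20% subgroup of 600 children. They are not power for a between-subgroup difference and were not updated to the section 8 size. Sections 6.1.2.1 and 9.2 cannot both stand. These conclusions rest on the text and the table rows alone.

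The sizes are approximate. They rest on normal or t approximations rather than the plan's simulations, whose code is not given, and on an assumed two-sided test. Navigator power within the subgroup falls from about 0.85 to about 0.72 for cells a to d. The SAP defines "the marginal effect of the navigator intervention (a+c+e vs b+d+f" as the full navigator contrast, so the fall is smaller if cells e and f contribute; their size is not given, and it would take 600 − 432 = 168 such children to restore 0.85. School power falls by about 4 to 8 points. The between-subgroup figures of 0.77 and 0.63 are illustrative only.

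The primary analysis is untouched. The effect is on how null moderator results for Aim 2a are read and, separately, on whether the bootstrap bounds in 6.1.3 are correctly described.

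**What to change.** 1. In SAP 6.1.6, relabel the 88% and 83% as design-phase, within-subgroup power at n=600, not updated to the section 8 size, and add that they are not power for a difference between subgroups.
2. In SAP 6.1.2.1, delete the clause that credits effect-modifier contrasts with good power, together with its forward reference, so that the section agrees with 9.2.
3. In SAP 6.1.3, replace the order-statistic statement with the 10th and 390th of 399 resamples, or the 25th and 975th of 999.
4. Optional: note in 6.1.6 that both within-subgroup powers are lower at n=432, marked as an approximation (navigator about 0.85 to about 0.72 for cells a to d, less of a fall if cells e and f contribute; school about 4 to 8 points lower). Any between-subgroup figure should be marked illustrative, with its assumed split and difference, and as before Bonferroni.

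The cost is a few sentences of SAP text. No model, contrast, test or sample size changes.

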5.1.3 Patient-level analysis – marginal models

Second, marginal models using generalized estimating equations (Fitzmaurice 2011) will produce robust estimates that adjust for clustering at the school level. These methods tend to be robust for

non-continuous outcomes (non-identify link models) and those outcomes will likely apply to our outcomes of asthma control (possibly a log gamma model) and number of symptom days (possibly a log link Poisson or negative binomial model). In contrast to mixed effects models, marginal models do not rely on numerical integration. In addition to generalized estimating equations, quasi-least squares regression (Shults and Hilbe, 2014) will also be implemented. Quasi-least squares regression is an approach for estimation of the correlation parameters that is in the framework of generalized estimating equations; it allows for application of correlation structures that were previously unavailable for generalized estimating equations and can sometimes be implemented when generalized estimating equations fails to converge.

Marginal models tend to work poorly for designs with small numbers of clusters. In our case, the number of clusters (36) is relatively large. Nevertheless, we shall implement at least one method for adjusting for a number of clusters that is not large, as implemented in Stata's program xtgeebcv program (Gallis 2019) and R's program "saws" (Fay and Graubard 2001).

5.1.4 School-level analysis -- randomization-test-based methods.

Third, assumption-free, randomization-test-based (permutation test) methods that do not rely on assumptions of parametric models will also be applied. (Berger, 2000; Good, 2005; Small, 2008; Tang 2009; Rosenbaum 2002). (Also see Hayes and Moulton 2017)

We will use conventional levels of statistical significance (p=0.05) for all pre-specified comparisons for these aims. We shall not apply Bonferroni corrections for estimates from different modeling methods that use the same specification.

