6.1.2.1 Record linkage for patient's home address and ADI 12-digit FIPS code

Effective Spring 2020, CHOP EPIC system will geocode all patient's addresses into 12-digit FIPS codes. These codes will be downloaded from EPIC for each patient for the patient's address at the time of enrollment. Following changes in address will be too complex, and for that reason the address at the time of enrollment will be used. Record linkage with the ADI will proceed based on the 12-digit FIPS codes in EPIC and the ADI database.

Using this information, we will use the ADI index as a proxy for the neighborhood characteristics listed in Table 6.1b.

Patient utilization at baseline: Value in looking at by severity of exacerbation as the relevant outcome that is subject to modification. Whether to hospitalize a patient or to go to the emergency department are often judgment calls and therefore might be vary with the same level of exacerbation. Nevertheless, although baseline utilization might modify the effect of the intervention, the direction of that modification is uncertain. This analysis is therefore hypothesis generating.

We will reserve looking at outcomes until we have settled on candidate effect modifiers and using (or developing) indexes or summary measures.

We shall investigate treatment effect heterogeneity by using carefully pre-specified factors measured at baseline. Post baseline factors that might affect outcomes will fall under the topic of "mediation" (see below) and will be handled differently.

Because these key potential effect modifiers vary within the unit of randomization (school), these contrasts are essentially within-cluster comparisons with good statistical power (see below). Effect modification (moderation) can be estimated using the mixed effects and longitudinal models outlined previously without additional complexity. In all cases, effect modifiers (moderators) will be specified before the start of analysis to address concerns about multiple comparisons.

As of this writing, guidelines remain for publication on proper characterization of subgroups and the analysis of effects by subgroup. In brief, the following principles apply.

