9.1 Multiple comparisons

Adjustments in critical levels for determining "statistical significance" when requested will follow these principles.

(a) If the contrast of interest is a primary or secondary outcome and pre-specified as such, we will make no adjustment

(b) All ad hoc, post SAP analyses and contrasts will be exploratory and hypothesis generating.

(c) All analyses for effect modification and mediation will consider the number of comparisons and make adjustments using simple Bonferroni correction for critical p-values.

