9.2 Statistical power

It is very likely that all attempts to demonstrate heterogeneity of treatment effect and/or mediation will fail owing to inadequate numbers of patients spread over a large number of schools.

10. Update to Data Analysis Plan: Impact of Pandemic Restrictions. Presented to and approved by Data Safety Monitoring Board (DSMB) on 6/29/2021:

The original statistical analysis plan (SAP) includes the fitting of longitudinal models to evaluate the impact of study interventions on primary and secondary outcomes in models that model time as months from randomization, with splines (knots at 0, 3, 6, 9 and 12 months) and time by treatment interaction terms. Mixed-effects and population-averaged (GEE) models will be fitted.

The initial analyses will be conducted as planned. **Sensitivity analyses** will then be performed to evaluate the impact of pandemic restrictions (pre and post^{*}, where *Post = Time Period after March 14, 2020).

Longitudinal models for the main analyses will be modified to include an indicator variable for post COVID-19 phase* with time by post Covid-19 interaction and time by post COVID-19 by intervention interaction terms. In these models, post Covid-19 phase will be included as a time varying covariate within individuals.

Post pandemic restrictions by time by intervention interaction terms: If significant, the impact of an intervention at a particular time point (e.g., at 3 months post-randomization) depends on post pandemic status (relative to pre).

Post pandemic restrictions by time terms: If significant, the expected value of the outcome at a particular time point depends on post pandemic status (relative to pre).

Post pandemic restrictions indicator variable: If significant, the expected value of the outcome variables depends on post pandemic status (relative to pre).

References:

Berger VW. Pros and cons of permutation tests in clinical trials. Stat Med. 2000; 19(10):1319-28. [PMID: 10814980]

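### SAP 6.1.6 and 9.1(c) fix single-step Bonferroni for the moderator and mediation tests; Holm's step-down gives the same 5% family-wise control and never rejects less, a free but usually small gain

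*SAP*

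**What the plan says.** SAP 6.1.6, after giving power for a 20% subgroup, says of multiplicity: "To the extent that the study reports differences in outcomes by baseline groups, simple Bonferroni corrections will apply". Section 9.1(c) covers both halves of Aim 2: "All analyses for effect modification and mediation will consider the number of comparisons", and the analyses will "make adjustments using simple Bonferroni correction for critical p-values". No stepwise procedure is named anywhere in the SAP. The significance level, from 5.1.4, is 0.05; sidedness is not stated.

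The number of comparisons is not fixed. Table 6.2.3 lists candidate mediators, and 6.2.1 allows some to be dropped or reclassified on timing. Table 6.1b lists child-level moderators that are to be condensed into an unspecified small number of latent classes.

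On power, the SAP speaks in two voices. Section 6.1.2.1 says of child-level moderators that "these contrasts are essentially within-cluster comparisons with good statistical power", and 6.1.6 says "our design has 88% power to detect the effect of the navigator and 83% power to detect the effect of school", while noting that multiplicity is left out of those figures. Section 6.3 warns: "Power will quickly degrade with more than a few candidate mediators". Section 9.2 goes further: "It is very likely that all attempts to demonstrate heterogeneity of treatment effect and/or mediation will fail owing to inadequate numbers of patients".

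**The concern.** Single-step Bonferroni holds every test at 0.05/m, however many of the others have already been rejected. Holm orders the p-values and compares them with 0.05/m, 0.05/(m−1), and so on up to 0.05, stopping at the first failure. It uses the same p-values and gives the same error guarantee. Where two procedures have equal protection and one never rejects less, choosing the other gives power away for nothing, and Aims 2a and 2b are where the SAP itself worries about power. What is at stake is the chance of detecting second and later moderators or mediators once one has been found. The contrasts for primary and secondary outcomes are untouched, because 9.1(a) leaves them unadjusted.

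**Working it through.** **Inputs.** Alpha 0.05 (SAP 5.1.4), taken as two-sided. Single-test power before adjustment: 0.88 for the navigator and 0.83 for school in a subgroup of 120 (SAP 6.1.6); above 0.8 for the mediation effects considered in SAP 6.3. I add 0.30 and 0.50 as assumptions, to represent the shortage described in SAP 9.2. Family size m is an assumption: 11 is a count of Table 6.2.3 (7 patient-level and 4 school-level rows), and 2 stands for a much reduced family.

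**The plan's own figures.** Take 60 children per arm, SD 1 and power = Φ(d·√(n/2) − 1.96).
- School: d = 0.6 with 22 schools gives a design effect of 1 + (120/22 − 1)·0.06 = 1.267, n = 60/1.267 = 47.4 and power 0.83. This matches.
- Navigator: d = 0.50 gives 0.78, 0.55 (adding half the interaction) gives 0.85 and 0.60 gives 0.91, so 0.88 is not reproduced. The SAP's figure comes from a custom simulation whose model is not given. I do not call it wrong, and nothing below depends on it.

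**Why Holm dominates.** At step i its threshold is 0.05/(m − i + 1), which is never below 0.05/m, so every Bonferroni rejection is also a Holm rejection. With m0 true nulls, the first true null to be rejected is tested when at least m0 hypotheses remain, so its threshold is at most 0.05/m0. Summing over the m0 nulls bounds the family-wise error by 0.05 whatever the dependence. Step 1 uses 0.05/m in both procedures, so the chance of at least one rejection is identical.

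**What Bonferroni costs.** The expected z is δ = 1.96 + z(single-test power), and adjusted power is Φ(δ − c), where c is the two-sided critical value at 0.05/m. For m = 2, c = 2.241; for m = 11, c = 2.838. Single-test power of 0.88 (δ = 3.135) falls to 0.81 with m = 2 and 0.62 with m = 11. Power of 0.83 (δ = 2.914) falls to 0.75 and 0.53.

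**What Holm returns, m = 11.** I simulated 200,000 families of independent z-tests per scenario. Entries are power per real effect, Bonferroni to Holm.

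| Single-test power | 3 real | 6 real | 11 real |
|---|---|---|---|
| 0.30 | 0.081 to 0.082 | 0.080 to 0.082 | 0.081 to 0.085 |
| 0.50 | 0.189 to 0.193 | 0.190 to 0.199 | 0.190 to 0.211 |
| 0.80 | 0.485 to 0.498 | 0.486 to 0.522 | 0.485 to 0.593 |
| 0.83 | 0.531 to 0.546 | 0.531 to 0.570 | 0.530 to 0.652 |

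Holm contained every Bonferroni rejection in every run, and the chance of any rejection was the same. With at least one real effect, Holm's simulated family-wise error was at most 0.048; with all 11 null, both procedures gave 0.0496. With correlation 0.4 and 6 real effects, the gain is 0.5 point at single-test power 0.30 and 1.4 points at 0.50.

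**m = 2, both real, by formula.** Write a for power at 0.025 and b for power at 0.05. Holm's power per effect is a + (b − a)·a.
- At 0.83: 0.749 + (0.830 − 0.749)·0.749 = 0.81, against 0.75.
- At 0.30: 0.210 + (0.300 − 0.210)·0.210 = 0.23, against 0.21.

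**The case against.** The strongest reply is that Holm helps least where the SAP says help is needed. With 11 independent tests, 6 real effects and single-test power of 0.30, the gain is 0.2 point; at 0.50 it is about 0.9 point. Sizeable gains need many true effects that are also well powered, and SAP 9.2 does not expect that. The figures of 0.88, 0.83 and above 0.8 also assume 600 children, before section 8 lowered the projection to about 100 per cell. All of this stands, and it sets the size of the point.

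A second reply is that the SAP puts estimation first (section 9) and adjusts critical levels only when testing is requested, and that Bonferroni has simple matching simultaneous intervals while Holm does not. That is a real property, but the plan does not use it: 6.1.3 specifies plain 95% percentile bootstrap intervals, and 9.1(c) adjusts critical p-values only.

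A third reply is that a family of 11 is not the SAP's number. This is also right. A reader might infer that each mediation test is held at 0.05/11 = 0.0045. The documents do not support that as fact, because Table 6.2.3 is a candidate list that 6.2.1 can shorten. The size of the family also matters more than the procedure in most of these scenarios: under Bonferroni at the stated 0.88, moving from 2 to 11 tests takes per-test power from 0.81 to 0.62.

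**Conclusion.** The point holds as a free improvement of low priority. Single-step Bonferroni is valid and introduces no error or bias, but Holm uniformly dominates it for the tests that 6.1.6 and 9.1(c) cover. Under the assumption of 11 independent, equally powered two-sided tests, the gain per real effect is about 4 points with 6 real effects, and 11 to 12 points if all 11 are real, at single-test power of 0.80 to 0.83. With 2 tests, both real, it is about 6 points at 0.83 and 2 points at 0.30. With 11 tests, single-test power of 0.30 to 0.50 and 6 or fewer real effects, it is at most about 1 point (1.4 points with correlation 0.4).

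A reader might infer that Holm would rescue Aims 2a and 2b from the power shortage that the SAP describes. It would not: it cannot raise the chance of at least one rejection, and if all attempts fail the two procedures report the same thing.

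**What to change.** In SAP 6.1.6 and 9.1(c), replace the simple Bonferroni correction with *the Holm step-down procedure at 5%*, applied to the same set of comparisons that the Bonferroni count would have used. State that this set will be listed and fixed before outcomes are seen; either procedure needs that list, since without it the thresholds are undefined. How the comparisons are grouped into families is a separate decision, which this change does not make for the SAP.

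The cost is one phrase in two sections plus the list. No new data, models or p-values are needed, and the estimates and planned 95% bootstrap intervals stay as they are. The only loss is simple matching simultaneous intervals, which the SAP does not plan. Because the SAP carries a finalisation date of September 13, 2022, the change should be a dated amendment made before any moderator or mediator result is seen. The documents do not show whether that is still possible.
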